**Dose modification and toxicity management of infusion-reactions related to pembrolizumab**

Pembrolizumab may cause severe or life-threatening infusion-reactions including severe hypersensitivity or anaphylaxis. Signs and symptoms usually develop during or shortly after drug infusion and generally resolve completely within 24 hours of completion of infusion. Dose modification and toxicity management guidelines for pembrolizumab associated infusion reactions are provided in [Table 5](#).

Table 5 Pembrolizumab Infusion Reaction Dose Modification and Treatment Guidelines

NCI CTCAE Grade	Treatment	Premedication at Subsequent Dosing

Grade 1  Mild reaction; infusion interruption not indicated; intervention not indicated
	
Increase monitoring of vital signs as medically indicated until the subject is deemed medically stable in the opinion of the investigator.
	
None

Grade 2  Requires therapy or infusion interruption but responds promptly to symptomatic treatment (eg, antihistamines, NSAIDs, narcotics, IV fluids); prophylactic medications indicated for <math>\leq 24</math> h
	
Stop Infusion.  Additional appropriate medical therapy may include but is not limited to:  IV fluids  Antihistamines  NSAIDs  Acetaminophen  Narcotics  Increase monitoring of vital signs as medically indicated until the subject is deemed medically stable in the opinion of the investigator.  If symptoms resolve within 1 hour of stopping drug infusion, the infusion may be restarted at 50% of the original infusion rate (eg, from 100 mL/h to 50 mL/h). Otherwise dosing will be held until symptoms resolve and the subject should be premedicated for the next scheduled dose.  Subjects who develop Grade 2 toxicity despite adequate premedication should be permanently discontinued from further study drug treatment
	
Subject may be premedicated 1.5 h (<math>\pm 30</math> minutes) prior to infusion of pembrolizumab with:  Diphenhydramine 50 mg po (or equivalent dose of antihistamine).  Acetaminophen 500-1000 mg po (or equivalent dose of analgesic).

NCI CTCAE Grade	Treatment	Premedication at Subsequent Dosing

Grades 3 or 4            Grade 3:            Prolonged (ie, not rapidly responsive to symptomatic medication and/or brief interruption of infusion); recurrence of symptoms following initial improvement; hospitalization indicated for other clinical sequelae (e.g., renal impairment, pulmonary infiltrates)            Grade 4:            Life-threatening; pressor or ventilatory support indicated
	
Stop Infusion.            Additional appropriate medical therapy may include but is not limited to:            Epinephrine**            IV fluids            Antihistamines            NSAIDs            Acetaminophen            Narcotics            Oxygen            Pressors            Corticosteroids            Increase monitoring of vital signs as medically indicated until the subject is deemed medically stable in the opinion of the investigator.            Hospitalization may be indicated.            **In cases of anaphylaxis, epinephrine should be used immediately.  Subject is permanently discontinued from further study drug treatment.
	
No subsequent dosing

Abbreviations: CTCAE=Common Terminology Criteria for Adverse Events, IV=intravenous, NCI=National Cancer Institute, NSAID=nonsteroidal anti-inflammatory drug            Appropriate resuscitation equipment should be available at the bedside and a physician readily available during the period of drug administration.            For further information, please refer to the Common Terminology Criteria for Adverse Events v4.0 (CTCAE) at http://ctep.cancer.gov
		

### **Other allowed dose interruptions for pembrolizumab**

Pembrolizumab may be interrupted for situations other than treatment-related AEs such as medical/surgical events or logistical reasons not related to study therapy. Subjects should be placed back on study therapy within 3 weeks of the scheduled interruption, unless otherwise discussed with the Sponsor. The reason for interruption should be documented in the patient's study record.

#### **5.2.1.2.2 Chemotherapeutic agents (etoposide/platinum)**

Study drug-related toxicities must be resolved to baseline or Grade  $\leq 1$  (with the exception of alopecia, Grade 2 fatigue, and endocrine-related AEs requiring treatment or hormone replacement, which may be Grade  $\leq 2$ , and creatinine clearance, for which the guidelines provided below may be followed) prior to administering the next dose. Subjects must not receive the next cycle of chemotherapy if any of the following apply:

- Absolute neutrophil count (ANC)  $< 1,500/\text{mm}^3$
- Platelet count  $< 100,000/\text{mm}^3$
- Hemoglobin level  $< 8 \text{ g/dL}$
- Total bilirubin level  $> 1.5 \times \text{ULN}$
- Aspartate aminotransferase (AST) and alanine aminotransferase (ALT) levels  $\geq 2.5 \times \text{ULN}$ , or  $\geq 5 \times \text{ULN}$  if liver metastases are present

Recommended dose modifications for key chemotherapy toxicities (etoposide and cisplatin/carboplatin) are outlined in [Table 6](#) and [Table 7](#). These serve as a guide and do not replace investigator judgment and applicable local label recommendations, if more stringent. A subject is allowed to switch from cisplatin to carboplatin if the subject develops unexpected toxicities with the use of cisplatin (including hearing loss), becomes ineligible for further cisplatin therapy, and/or the investigator considers switching to carboplatin to be in the best interest of the subject.

A maximum of 2 dose reductions per chemotherapy agent are permitted; if additional reductions are required, that particular agent must be discontinued. Once the dose has been decreased, it should remain reduced for all subsequent administrations or be further reduced, if necessary. There will be no dose escalations in this study. Each chemotherapy cycle may not be delayed by more than 3 weeks ( $> 21$  consecutive days) despite supportive treatment. If unacceptable toxicities related to etoposide, cisplatin, or carboplatin occur, and only one of the agents is thought to be causing a specified toxicity leading to a 21-day delay of administration of the next cycle, as determined by investigator judgment, the agent will be discontinued but the other drugs may be continued.

Table 6 Recommended Chemotherapy Dose Modifications for Hematological Toxicity

Drug Related Toxicitya	Etoposide	Cisplatin	Carboplatin
	Dose Level (DL) from Table 3		
Neutrophils (ANC) <500/mm  without fever	DL -1	DL -1	DL -1
Febrile neutropenia (fever ≥38.5°C and ANC <1,000/mm  )	DL -1	DL -1	DL -1
Platelets <50,000/mm  without significant bleeding or requiring blood transfusion	DL -1	DL -1	DL -1
Platelets <50,000/mm  with Grade ≥2 hemorrhage or requiring blood transfusion	DL -2	DL -2	DL -2
Grade 4 hemoglobin	DL -1	DL -1	DL -1
Abbreviations: ANC=absolute neutrophil count, DL=dose level  Note: If toxicity can clearly be attributed to one of the drugs, the investigator may choose to only reduce the dose of one of the chemotherapy agents. Investigators may decide to use supportive measures/treatment and/or secondary prophylaxis as per institutional standards (eg, filgrastim, pegfilgrastim, transfusions) instead of dose reductions for the next cycle, if considered in the best interest of the subject.  a Should the hematologic toxicity recur, the dose of the agent could be reduced further. However, not more than 2 dose reductions per chemotherapy agent are permitted.			

**Table 7 Recommended Chemotherapy Dose Modifications for Non-hematologic Toxicity**

Drug Related Toxicitya	CTCAE Grade	Etoposide	Cisplatin	Carboplatin
		Dose Level (DL) from Table 3		
Nausea/vomiting	Grade $\geq 3^b$	DL 0	DL -1	DL -1
Mucositis	Grade $\geq 3^b$	DL -1	DL -1	DL -1
Diarrhea	Grade $\geq 3^b$	DL -1	DL -1	DL -1
Peripheral neuropathy	Grade 2	No modification	DL -1 c	No modification
	Grade 3	No modification	Discontinue d	DL -1
	Grade 4	No modification	Discontinue	DL -1
Total bilirubin	Grade 2	DL -2	No modification	No modification
	Grade 3	Discontinue	No modification	No modification
	Grade 4	Discontinue	No modification	No modification
AST or ALT Elevation	Grade 3	DL -1	DL -1	DL -1
	Grade 4	Discontinue	Discontinue	Discontinue
Other Non-hematologic Toxicity (except fatigue and transient arthralgia and myalgia)	Grade $\geq 3$	DL -1	DL -1	DL -1

Note: If considered in the best interest of the subject, and consistent with local practice, investigators may decide to use supportive measures/treatment, and/or secondary prophylaxis instead of dose reductions for the next cycle. Also, if toxicity can clearly be attributed to one of the drugs, the investigator may choose to only reduce the dose of one of the chemotherapy agents.

a Should the toxicity recur, the dose of the agent could be reduced further. However, not more than 2 dose reductions per chemotherapy agent are permitted.

b The first occurrence of Grade  $\geq 3$  nausea/vomiting, mucositis, and diarrhea should be managed symptomatically with optimal medical therapy, and improve to Grade  $\leq 1$  prior to proceeding with additional therapy. Should these events recur despite aggressive management, a dose modification can be employed once the AE improves to Grade  $\leq 1$ .

c If Grade 2 neurotoxicity recurs after DL -1, drug will be given at DL -2 or switch can be made to the appropriate dose of carboplatin at the discretion of the investigator in consultation with the Sponsor. If Grade 2 neurotoxicity persists after 2 dose level reductions and 21-day hold, switch can be made to the appropriate dose of carboplatin at the discretion of the investigator in consultation with the Sponsor.

d If Grade 3 neurotoxicity occurs, cisplatin will be discontinued and, upon improvement, a switch can be made to the appropriate dose of carboplatin at the discretion of the investigator in consultation with the Sponsor.

**Creatinine clearance:**

Creatinine clearance (CrCl) will be based on either the Cockcroft-Gault formula (Section 5.2.2.2.1) or another acceptable standard formula.

For patients receiving cisplatin, the scheduled dose of cisplatin may only be administered if the calculated CrCl is  $\geq 50$  mL/min:

- If CrCl falls to  $< 50$  mL/min, delay the start of that cycle for  $\leq 21$  days. In the interim, monitor renal function weekly and consider intravenous (IV) hydration. When CrCl improves to  $\geq 50$  mL/min, decrease cisplatin to dose level (DL) -1 (Table 3). Alternatively, if in the investigator's judgment it is in the best interest of the patient, cisplatin can be switched to carboplatin if the calculated CrCl is appropriate, and in consultation with the Sponsor.
- At the second occurrence of CrCl  $< 50$  mL/min, decrease cisplatin to DL -2 upon improvement of CrCl to  $\geq 50$  mL/min. Alternatively, if in the investigator's judgment it is in the best interest of the patient, cisplatin can be switched to carboplatin if the calculated CrCl is appropriate, and in consultation with the Sponsor.
- At the third occurrence of CrCl  $< 50$  mL/min, cisplatin should be discontinued. If in the investigator's judgment it is in the best interest of the patient, cisplatin can be switched to carboplatin if the calculated CrCl is appropriate, at the discretion of the investigator and in consultation with the Sponsor.

For patients receiving carboplatin, the scheduled dose of carboplatin may only be administered if the calculated CrCl is  $\geq 40$  mL/min:

- If CrCl falls to  $< 40$  mL/min, delay the start of that cycle for  $\leq 21$  days. In the interim, monitor renal function weekly and consider IV hydration. When CrCl improves to  $\geq 40$  mL/min, decrease carboplatin to DL -1 (Table 3).
- At the second occurrence of CrCl  $< 40$  mL/min, decrease carboplatin to DL -2 upon improvement of CrCl to  $\geq 40$  mL/min.
- At the third occurrence of CrCl  $< 40$  mL/min, carboplatin should be discontinued.

### **5.2.2 Timing of Dose Administration**

All trial treatments will be administered on an outpatient basis.

Trial treatment should be administered beginning on Day 1 of each cycle after all procedures and assessments have been completed (time points listed in Section 6). Day 1 of each cycle should occur as scheduled (or in a window of  $\pm 3$  days for administrative reasons only). Etoposide must be administered on 3 consecutive days without interruption (Days 1, 2, and 3) in Cycles 1 to 4.

For subjects who experience disease progression, investigators may elect to continue trial treatment until confirmation of disease progression or may elect to interrupt treatment by deferring the decision to continue/discontinue treatment in the trial until confirmation of disease progression per modified RECIST 1.1 at least 28 days from the date of imaging

demonstrating disease progression. Subjects for whom disease progression is not confirmed on subsequent imaging may resume treatment. Please see Section 5.8 for other exceptions.

### **5.2.2.1 Pembrolizumab (or Saline Placebo)**

Pembrolizumab or saline placebo will be administered first in the sequence of medications. Upon completion of the pembrolizumab or saline placebo infusion, premedication for the chemotherapy should be administered as per local SOC, followed by chemotherapy.

Pembrolizumab or saline placebo will be administered as a 30-minute IV infusion Q3W on Day 1 of each cycle. Sites should make every effort to target infusion timing to be as close to 30 minutes as possible. However, given the variability of infusion pumps from site to site, a window of -5 minutes to +10 minutes is permitted (ie, infusion time is 25 to 40 minutes).

The Pharmacy Manual contains specific instructions for pembrolizumab dose calculation, reconstitution, infusion fluid preparation, and administration.

### **5.2.2.2 Chemotherapy**

Chemotherapy should be administered as described in the following subsections. Subjects are allowed to switch from cisplatin to carboplatin, if the subject becomes ineligible for further cisplatin therapy according to local guidelines and the investigator considers switching to carboplatin to be in the best interest of the subject.

#### **5.2.2.2.1 Carboplatin**

Carboplatin at a dose calculated to achieve an area under the plasma drug concentration time curve (AUC) of 5 will be administered as an IV infusion over approximately 60 minutes Q3W on Day 1 for 4 cycles. Carboplatin dose should not exceed 750 mg. AUC should be calculated using the Calvert formula:

- Total dose (mg) = (target AUC) × (CrCl + 25)
- The estimated CrCl in the Calvert formula should not exceed 125 mL/min
- Maximum carboplatin dose (mg) = target AUC 5 × (125 + 25)  
= 5 × 150  
= 750 mg

Creatinine clearance must be calculated using either the Cockcroft-Gault formula or another acceptable standard formula for estimating CrCl in mL/min based on serum creatinine:

- Men:  $[(140 - \text{age (y)}) \times \text{weight (kg)}] / [72 \times \text{serum creatinine (mg/dL)}]$
- Women:  $[(140 - \text{age (y)}) \times \text{weight (kg)}] \times 0.85 / [72 \times \text{serum creatinine (mg/dL)}]$

Note: Due to differences in serum creatinine units, sites may use either the standard Cockcroft-Gault formula or another acceptable standard formula used at their institution.

Dose may be rounded to the nearest 50 mg at the discretion of the investigator, and according to institutional standards.

Unless there is a change in weight >10%, the same dose of carboplatin can be used throughout the 4 cycles (provided there are no additional toxicities).

Additional premedications should be administered as per standard practice.

#### **5.2.2.2.2 Cisplatin**

Cisplatin 75 mg/m^2 will be administered as an IV infusion Q3W on Day 1 for 4 cycles. An infusion time of 60 minutes is recommended, but cisplatin may be administered over 30 to 180 minutes to accommodate local SOCs. Body surface area (BSA) will be obtained using the Dubois and Dubois or Mosteller formula. The BSA calculated on Cycle 1, Day 1 of therapy can be used throughout the 4 cycles, unless there is a change in weight >10%. Cisplatin will be given for up to 4 cycles. Additional premedications should be administered as per standard practice.

#### **5.2.2.2.3 Etoposide**

Etoposide 100 mg/m^2 will be administered as an IV infusion Q3W on Days 1, 2, and 3 of Cycles 1 to 4. Days 1, 2, and 3 must be consecutive days without interruption. An infusion time of 30 to 60 minutes is recommended, but etoposide may be administered over 30 to 120 minutes to accommodate local standards of care. Body surface area will be obtained using the Dubois and Dubois or Mosteller formula. The BSA calculated on Cycle 1, Day 1 of therapy can be used throughout the 4 cycles, unless there is a change in weight >10%. Additional premedications should be administered as per standard practice.

### **5.2.3 Trial Blinding**

This is a double-blinded trial with respect to pembrolizumab and placebo treatment. The subject, the investigator, and Sponsor personnel or delegate(s) who are involved in the treatment administration or clinical evaluation of the subjects will be unaware of the treatment assignments. The chemotherapy agents will be open-label. Pembrolizumab will be supplied to the sites in an open label manner. The study site's unblinded pharmacist will obtain each subject's study identification number and study drug assignment from the interactive voice response system/integrated web response system (IVRS/IWRS) and prepare the solutions for infusion. The unblinded pharmacist will provide the investigative staff with ready-to-use blinded pembrolizumab or saline placebo infusion solutions, packaged identically in order to maintain the blinding, for administration at scheduled infusion visits. In addition to emergency unblinding for severe or life-threatening AEs with potential immunologic etiology, non-emergency unblinding to pembrolizumab versus placebo administration may occur on an individual subject basis and only after consultation with the Sponsor at the time of (1) centrally verified disease progression and subject has discontinued all study treatments or, (2) when the subject has discontinued all study treatments and a new anti-cancer treatment is going to be started. Non-emergency unblinding, only after

consultation and approval from the Sponsor, is implemented through interactive response technology (IRT) by following the instructions in the IRT site user manual.

Additionally, imaging data will be centrally reviewed by radiologists who are blinded to subject treatment assignment, and the allocation schedule will be blinded in the database, preventing aggregate analysis.

See Section 7.1.4.2, Blinding/Unblinding, for a description of the method of unblinding a subject during the trial, should such action be warranted.

### **5.3 Randomization**

Treatment randomization will occur centrally using an interactive voice response system / integrated web response system (IVRS/IWRS). There are 2 treatment arms. Subjects will be assigned randomly in a 1:1 ratio to pembrolizumab + EP or placebo + EP. Prior to randomization, the investigator's choice of platinum agent (cisplatin or carboplatin) will be documented in the IVRS/IWRS system.

### **5.4 Stratification**

Treatment randomization will be stratified according to the following factors:

- Type of platinum therapy (carboplatin or cisplatin)
- Baseline ECOG performance status (0 or 1)
- Baseline LDH ( $\leq$  or  $>$ ULN)

### **5.5 Concomitant Medications/Vaccinations (Allowed & Prohibited)**

Medications or vaccinations specifically prohibited in the exclusion criteria are not allowed during the ongoing trial. If there is a clinical indication for any medication or vaccination specifically prohibited during the trial, discontinuation from trial therapy or vaccination may be required. The investigator should discuss any questions regarding this with the Sponsor Clinical Director. The final decision on any supportive therapy or vaccination rests with the investigator and/or the subject's primary physician. However, the decision to continue the subject on trial therapy or vaccination schedule requires the mutual agreement of the investigator, the Sponsor and the subject.

#### **5.5.1 Acceptable Concomitant Medications**

All treatments that the investigator considers necessary for a subject's welfare may be administered at the discretion of the investigator in keeping with the community standards of medical care. All concomitant medications will be recorded on the electronic case report form (eCRF) including all prescription, over-the-counter (OTC), herbal supplements, and IV medications and fluids. If changes occur during the trial period, documentation of drug dosage, frequency, route, and date will also be included on the eCRF.

Palliative and supportive care is permitted during the course of the trial for underlying medical conditions and management of symptoms. Surgery or radiotherapy for tumor control is not permitted during the study; however, radiotherapy or procedures for symptom management are allowed.

All concomitant medications received within 28 days before the first dose of trial treatment and up to 30 days after the last dose of trial treatment should be recorded. Concomitant medications administered more than 30 days after the last dose of trial treatment should be recorded for SAEs and events of clinical interest (ECIs) as defined in Section 7.2.

### **Colony-Stimulating Factors**

The use of colony-stimulating factors (CSFs) is highly recommended as primary prophylaxis to reduce the risk of febrile neutropenia in this patient population, especially as many subjects have multiple co-morbidities and advanced disease. The American Society of Clinical Oncology guidelines for use of CSFs should be followed for this trial [112].

### **Antiemetic therapy**

Antiemetic therapy should follow the Multinational Association of Supportive Care in Cancer guidelines [113].

### **5.5.2 Prohibited/Restricted Concomitant Medications**

Subjects are prohibited from receiving the following therapies during Screening, Initial Treatment Phase, and Second Course Phase of this trial:

- Antineoplastic systemic chemotherapy or biological therapy
- Immunotherapy not specified in this protocol
- Investigational agents other than pembrolizumab
- Surgery for tumor control
- Radiation therapy

Note: Subjects are allowed to receive palliative radiotherapy for painful bone lesions. Targeted external beam irradiation should not be used in the primary lung field where assessment for tumor is indicated.

Note: PCI is permitted in subjects achieving CR or PR after Cycle 4.

- Live vaccines within 30 days prior to the first dose of trial treatment and while participating in the trial (eg, measles, mumps, rubella, varicella/zoster, yellow fever, rabies, BCG, and typhoid vaccine); seasonal influenza vaccines for injection are generally killed virus vaccines and are allowed; however, intranasal influenza vaccines (eg, FluMist®) are live attenuated vaccines and are not allowed

- Systemic glucocorticoids for any purpose other than:
  - To modulate symptoms of an AE that is suspected to have an immunologic etiology
  - As required during and after PCI (subjects requiring chronic glucocorticoid use following PCI should be discontinued from study therapy)
  - As needed for the prevention of emesis (as outlined in Section 5.5.1)
  - For topical use or ocular use
  - Premedication for IV contrast allergies
  - For inhalation in the management of asthma or chronic obstructive pulmonary disease

Subjects who, in the assessment of the investigator, require the use of any of the aforementioned treatments for clinical management should be removed from the trial. Subjects may receive other medications that the investigator deems to be medically necessary.

Other medications that are prohibited in this trial are discussed in Section 5.1.3.

There are no prohibited therapies during the Post-Treatment Follow-up Phase.

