- Combination method (requires use of 2 of the following):
  - Diaphragm with spermicide (cannot be used in conjunction with cervical cap/spermicide)
  - Cervical cap with spermicide (nulliparous women only)
  - Contraceptive sponge (nulliparous women only)
  - Male condom or female condom (cannot be used together)
  - Hormonal contraceptive: oral contraceptive pill (estrogen/progestin pill or progestin-only pill), contraceptive skin patch, vaginal contraceptive ring, or subcutaneous contraceptive injection

‡If a contraceptive method listed above is restricted by local regulations/guidelines, then it does not qualify as an acceptable method of contraception for subjects participating at sites in this country/region.

Subjects should be informed that taking the trial medication may involve unknown risks to the fetus (unborn baby) if pregnancy were to occur during the trial. In order to participate in

the trial, subjects of childbearing potential must adhere to the contraception requirement (described above) from the day of trial medication initiation (or 14 days prior to the initiation of trial medication for oral contraception) throughout the trial period up to 120 days after the last dose of pembrolizumab and up to 180 days after last dose of chemotherapeutic agents. If there is any question that a subject of childbearing potential will not reliably comply with the requirements for contraception, that subject should not be entered into the trial.

If a female subject inadvertently becomes pregnant while on treatment in this study, the subject will immediately be removed from the study. The site will contact the subject at least monthly and document the subject's status until the pregnancy has been completed or terminated. The outcome of the pregnancy will be reported to the Sponsor without delay and within 24 hours if the outcome is an SAE (eg, death, abortion, congenital anomaly, or other disabling or life-threatening complication to the mother or newborn). The study investigator will make every effort to obtain permission to follow the outcome of the pregnancy and report the condition of the fetus or newborn to the Sponsor. If a male subject impregnates his female partner, the study personnel at the site must be informed immediately and the pregnancy reported to the Sponsor and followed as described above and in Section 7.2.

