## **5.8 Subject Withdrawal/Discontinuation Criteria**

### **5.8.1 Discontinuation of Treatment**

Discontinuation of trial treatment does not represent withdrawal from the trial.

As certain data on clinical events beyond treatment discontinuation may be/are important to the study, they must be collected through the subject's last scheduled follow-up, even if the subject has discontinued trial treatment. Therefore, all subjects who discontinue trial treatment prior to completion of the treatment period will still continue to participate in the trial as specified in Section 6.0 and Section 7.1.5.7.

Subjects may discontinue treatment at any time for any reason or be dropped from trial treatment at the discretion of the investigator should any untoward effect occur. In addition, a subject may be discontinued from trial treatment by the investigator or the Sponsor if treatment is inappropriate, the trial plan is violated, or for administrative and/or other safety reasons. Specific details regarding procedures to be performed at treatment discontinuation are provided in Section 7.1.4 – Other Procedures.

A subject must be discontinued from trial treatment but continue to be monitored in the trial for any of the following reasons:

- The subject or subject's legally acceptable representative requests to discontinue trial treatment.
- Confirmed radiographic disease progression, as outlined in Section 7.1.5 (exception if the Sponsor approves treatment continuation)

Note: Subjects with new asymptomatic brain metastasis may be eligible to continue study treatment at the discretion of the investigator after consultation with the Sponsor. Section 7.1.2.7.6 provides details regarding eligibility requirements and subsequent radiographic assessments.

- Unacceptable AEs, as described in Section 7.2
- Any progression or recurrence of any malignancy, or any occurrence of another malignancy that requires active treatment
- Intercurrent illness other than another malignancy as noted above that prevents further administration of treatment
- Recurrent Grade 2 pneumonitis
- Recurrent Grade 3 diarrhea
- A confirmed positive serum pregnancy test
- Noncompliance with trial treatment or procedure requirements
- Investigator's decision to withdraw the subject
- Completion of 35 cycles of trial treatments (approximately 2 years)

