### **5.8.2 Withdrawal from the Trial**

A subject must be withdrawn from the trial if the subject or subject's legally acceptable representative withdraws consent from the trial.

If a subject withdraws from the trial, they will no longer receive trial treatment or be followed at scheduled protocol visits.

Specific details regarding procedures to be performed at the time of withdrawal from the trial including the procedures to be performed should a subject repeatedly fail to return for scheduled visits and/or if the study site is unable to contact the subject, as well as specific details regarding withdrawal from Future Biomedical Research are outlined in Section 7.1.4 – Other Procedures.

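### Sections 5.5.2 and 5.7.2 take some subjects off the trial, where Section 5.8.1 and the follow-up sections only stop treatment; the two sentences need reconciling (minor)

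*Combined protocol and SAP*

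**What the plan says.** Two sentences in the protocol take subjects off the trial itself.

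- **Section 5.5.2** (prohibited therapies): subjects whom the investigator judges to "require the use of any of the aforementioned treatments for clinical management should be removed from the trial". The list includes non-study antineoplastic and immunotherapy, tumor surgery, most radiotherapy, live vaccines and most systemic glucocorticoids.
- **Section 5.7.2** (contraception): "If a female subject inadvertently becomes pregnant while on treatment in this study, the subject will immediately be removed from the study". The next sentence requires at least monthly contact until the pregnancy ends. It does not mention disease or survival follow-up.

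Other sections treat the same or similar situations as the end of treatment only.

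- **Section 5.5**, the parent of 5.5.2, says that "discontinuation from trial therapy or vaccination may be required" and leaves continuation to joint agreement.
- **Section 5.8.1** states that stopping treatment is not withdrawal from the trial, and introduces its list with "A subject must be discontinued from trial treatment but continue to be monitored in the trial for any of the following reasons". The list includes "A confirmed positive serum pregnancy test".
- **Section 5.8.2** requires withdrawal from the trial where the subject or the subject's "legally acceptable representative withdraws consent from the trial", and says that withdrawal ends scheduled follow-up.
- **Section 1.0** (Trial Summary) has all subjects followed by telephone for survival until death, withdrawn consent or study end.
- **Sections 7.1.5.3.2 and 7.1.5.7** keep subjects who stop treatment without progression in PFS follow-up. **Section 7.1.5.3.3** moves those with progression or non-study anti-cancer therapy to survival follow-up.

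**The concern.** A site reading 5.5.2 or 5.7.2 alone is told to take the subject off the trial, and 5.8.2 gives leaving the trial a defined consequence: scheduled follow-up stops. Overall survival is a primary endpoint analysed by intention to treat, and Section 8.4.1 censors subjects without a documented death at last known contact. Some triggers in 5.5.2, such as a need for non-study systemic therapy or tumor surgery, may reflect deterioration. If contact ended at that point, censoring would be early and could be informative. The pregnancy conflict is the plainer contradiction, but it has negligible weight for survival.

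**Working it through.** **Comparison of the text**

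| Situation | One instruction | The other | Result |
|---|---|---|---|
| Pregnancy on treatment | 5.7.2: off the study | 5.8.1: off treatment, monitoring continues | Direct contradiction on the same event |
| Prohibited therapy needed | 5.5.2: off the trial | 5.8.1: stopping treatment is not withdrawal; 1.0: all subjects followed for survival; 7.1.5.3.2 and 7.1.5.3.3: follow-up continues | Conflict if 5.5.2 is read literally |
| Prohibited therapy needed | 5.5.2: off the trial | 5.5: trial therapy may have to stop | Different consequence; 5.5 is silent on follow-up |

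Section 5.5.2 itself points to the likely intent. For steroids after cranial irradiation it says "subjects requiring chronic glucocorticoid use following PCI should be discontinued from study therapy", and it closes with "There are no prohibited therapies during the Post-Treatment Follow-up Phase". A follow-up phase in which any therapy is allowed presupposes that subjects who stop treatment can still be followed.

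**Scale: effect on timing only**

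The documents give no number of affected subjects, so only a cost per subject can be worked out.

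Inputs from Section 8.9: 453 subjects, 1:1; accrual over 14.5 months; control median OS 10 months; HR 0.65; dropout 1% per month. The hazards are λ = ln 2/10 = 0.0693 (control), 0.65 × 0.0693 = 0.0451 (experimental) and δ = 0.01. The actual enrolment pattern is not given, so accrual density g(a) proportional to a^(k−1) is assumed, for two values of k.

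Expected deaths per arm by month T are n ∫ g(a) · λ/(λ+δ) · [1 − exp(−(λ+δ)(T−a))] da. Dropouts use δ/(λ+δ) in place of λ/(λ+δ).

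| | Plan (Table 16) | k = 1 | k = 1.38 |
|---|---|---|---|
| Deaths, months 18 / 22 / 31 | 175 / 224 / 294 | 188.9 / 233.9 / 300.0 | 174.7 / 223.1 / 294.1 |
| Dropouts by month 31 | not given | 53.7 | 52.6 |
| Deaths at month 31, no dropout | not given | 328.4 | 320.9 |
| Deaths per month near month 31 | not given | about 5.4 | about 5.75 |

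The value k = 1.38 was chosen to approximate the plan's counts, so its agreement is not independent confirmation. The projection already absorbs about 53 dropouts, at a cost of 328.4 − 300.0 = 28.4 or 320.9 − 294.1 = 26.8 deaths.

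For a subject still followed s months after randomization, the chance of a later recorded death by month 31 is the same integral with T − a replaced by 31 − a − s, averaged over arms. For s = 3 and s = 6 it is 0.623 and 0.575 (k = 1), or 0.607 and 0.556 (k = 1.38). Losing one such subject has these effects:

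- k = 1: 300.0 − 0.62 = 299.4 deaths, still above 294, so no delay.
- k = 1.38: 294.1 − 0.61 = 293.5 deaths, 0.5 short; 0.5/5.75 = 0.09 months.
- If that subject would certainly have died by month 31: at most 1/5.4 = 0.19 or 1/5.75 = 0.17 months.

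This takes removal as unrelated to prognosis. It bounds the timing effect per subject and says nothing about bias.

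**The case against.** The strongest reply is that this is loose wording. The protocol often uses leaving the study to mean ending treatment. Section 5.8.1 lists an investigator's decision to withdraw the subject among reasons to stop treatment yet keep monitoring. Section 8.6.1.2 expects placebo subjects to discontinue from the study earlier because of progression, although progression leads to survival follow-up. A Section 6.2 footnote speaks of withdrawal from the main study where 7.1.5.5 means the Initial Treatment Phase. Section 5.7.2 keeps monthly contact, and the survival-status requests in 7.1.5.4 reach participants without a scheduled contact.

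Most of this stands, and it fixes the point as minor. It does not remove it. The protocol draws the distinction explicitly in places: 7.1.2.7.6 for symptomatic brain metastases, 7.1.4.2 for unblinded subjects, and 5.5.2 itself for steroids. A site therefore cannot be sure that the broader phrase means treatment only. The 7.1.5.4 requests are made at the Sponsor's discretion, and the monthly contact in 5.7.2 ends with the pregnancy.

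Three stronger readings are tempting but unsupported:

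- **That some subjects have no follow-up rule.** Those with neither progression nor new therapy fall under 7.1.5.3.2 and 7.1.5.7.
- **That 5.8.2 makes withdrawn consent the exclusive ground for leaving the trial.** It lists no other ground, but does not call this one exclusive.
- **That 5.5 requires continued follow-up.** It speaks only of trial therapy; the follow-up rules come from 5.8.1, 1.0 and 7.1.5.

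**Conclusion.** The text is wrong as written, and the consequence is minor. Sections 5.7.2 and 5.8.1 give incompatible instructions for pregnancy. Section 5.5.2, read literally, conflicts with 5.8.1, 1.0, 7.1.5.3.2 and 7.1.5.3.3. Harm requires a site to apply either sentence literally and stop contact.

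A reader might infer that the plan builds informative censoring into overall survival, or that power is at risk. The documents support neither. They show no subject lost this way and give no basis for the size or direction of a bias in the hazard ratio. The 294-death minimum for the final analysis (Section 8.7) protects event-driven power, although it would not correct informative censoring if that occurred. The timing figures rest on the Section 8.9 assumptions and the assumed accrual shapes; the textual contradiction rests on no assumption.

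**What to change.** Reword the two sentences in 5.5.2 and 5.7.2 to agree with 5.8.1 and 5.8.2, so that these subjects are not withdrawn from the trial unless consent is withdrawn. Follow-up should continue as applicable: disease status under 7.1.5.3.2 and 7.1.5.7 until progression or the start of new anti-cancer therapy, then survival under 7.1.5.3.3. Promising both kinds of follow-up to everyone would create a new conflict, because 7.1.2.7.2, 7.1.2.7.3, 7.1.5.3.2 and 7.1.5.7 end disease-status follow-up once new anti-cancer therapy starts. Whether and when treatment stops is left as the Sponsor defines it.

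Before the final OS analysis, identify any subject already removed under these sentences and, where consent stands, obtain survival status.

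The cost is two reworded sentences, a reminder to sites, and a status check that can use the existing 7.1.5.4 mechanism. No SAP figure changes.
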